1.0 Objectives / Specific Aims

Prostate cancer is the most prevalent non-cutaneous malignancy in men, responsible for approximately 30,000 deaths in 2013 (1). There are considerable and persistent racial disparities in prostate cancer outcomes. Prostate cancer disproportionately affects African American men in terms of incidence, morbidity, and mortality (1), even after adjustment for stage (2). African American men have a 2- to 3- times increased risk of developing prostate cancer and have a greater mortality rate compared to white men (2). Reduced access to health care services also contributes to racial disparities in prostate cancer outcomes, but even in equal access health care systems such as the Veterans Administration (VA), African American Veterans have higher serum prostate-specific antigen (PSA) values and higher-grade tumors than white Veterans (3, 4), even when presenting at the same stage of disease. Thus, access to health care is necessary but not sufficient for eliminating racial differences in prostate cancer outcomes. A better understanding of the biological mechanisms underlying these disparities is needed to develop strategies to overcome them.

Racial disparities in prostate cancer outcomes mirror racial differences in vitamin D levels (5). Several studies have shown that about 60% of African American men have sub-optimal levels of circulating 25(OH)D (6,7). For this reason, vitamin D₃ supplementation is likely to especially benefit these men. Vitamin D promotes the differentiation of prostate cancer cells and maintains the differentiated phenotype of prostate epithelial cells, raising the possibility that long-term vitamin D deficiency may contribute to the progression from subclinical prostate cancer to clinical disease (5), especially among African American men.

We propose to investigate: (a) the transcription and biological pathways that are especially relevant to prostate cancer disparities between African American and Caucasian men and (b) any significant differences in the molecular signature that exist in African American and Caucasian men in relation to their vitamin D levels.

The proposed studies will analyze transcriptional profiles and biological pathways in prostate tissue specimens obtained at time of prostate biopsy from these subjects, using bioinformatics analyses of RNA sequencing (RNA-seq) data. Implementation of the studies proposed in this application will allow us to test the central hypothesis that circulating levels of vitamin D significantly impact the transcriptional and biological profiles in prostate tissue samples from African American men.

To test our hypothesis we propose the following **Objectives**:

1. To utilize RNA-seq analyses to further demonstrate and identify a specific stress pattern signal that exists between African American and Caucasian men who are undergoing prostate biopsy. We have demonstrated initial findings that transcriptional profiles and biological pathways in the prostate are significantly different between African American and Caucasian subjects; the further elucidation as a result of these studies will allow us to identify the molecular underpinnings of health disparities in prostate cancer.

2. To identify changes in molecular signature that exist in African American and Caucasian men in relation to their vitamin D levels. We will assess ECM-receptor interaction, cell adhesion molecules (CAMs) and Pi3K-Akt signaling pathway according to serum levels as well as differences in those on supplementation.

3. Assess the above findings specifically as they relate to serum ancestry markers. We plan to assess the varying importance and relationship of specific markers of ancestry. Our population has significant proportions of pure African ancestry patients which will assist in this process.

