We set Caucasian subjects (17 samples) as the control and African American subjects (10 samples) as the test. The results of our analyses showed that 3107 genes were differentially expressed using a stringent (highly significant) FDR<0.1, and 8237 genes were differentially expressed using a less stringent (still significant) FDR<0.4. Pathway analysis using the 3107 differentially expressed genes highlight major differences between the two groups, with African American showing higher expression of genes associated with immune response and inflammation. It must be noted that our observations are consistent with a previous report (34) based on the analysis of prostate tissue-derived RNA, performed using Affymetrix microarrays. This analysis revealed enhanced expression - in tissue samples from African American subjects - of biological pathways that are linked to autoimmune diseases, allergies, and inflammatory diseases. Even at this preliminary stage the results of our RNA-seq studies support the existence of considerable biological differences within the prostate between African American and Caucasian men and suggest that overexpression of genes linked to the inflammatory process may very well contribute to the increased severity and faster progression of prostate cancer in African American men, even at the early stage of disease (33).

Stress Response and Allostatic Load:

Allostatic load defines a set of clinical and biochemical parameters that can be easily measured in a basic clinical setting (35). These parameters can be analyzed to gauge the level of stress experienced by each subject. These values reflect chronic, steady state levels of stress as well as failure to shut-off responses to acute stressors. To the best of our knowledge, there is only one published report of a correlation between allostatic load in African American subjects and specific biomarkers (36). This report identified the dopamine receptor gene, *DRD4*, and the serotonin transporter gene, *SLC6A4*, as indicators of stress, because of a non-supportive family environment. Interestingly, both of these genes were very significantly up-regulated (at a FDR<0.1) in prostate tissue samples from African American men. These considerations suggest that the prostate appears to be, even at the molecular level, a "sentinel" organ for chronic stress.

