The results of our RNA-seq analyses are consistent with our study objectives. These preliminary indications make us confident that the acquisition of additional RNA-seq data will allow us to strengthen the significance of our findings and help us identify specific pathways for possible targeted intervention.

Genomic technologies can be easily applied to the prostate tissue samples obtained from eligible subjects, undergoing prostate biopsy as part of their standard medical care. The results of our preliminary studies have already shown significant differences in the transcription profiles in prostate tissue samples between African American and Caucasian men. In addition, special emphasis will be given to RNA-seq analyses of Hypothalamic-Pituitary-Adrenal (HPA) -related transcription profiles, measurements of allostatic load and comparison of these profiles by race.

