10.0 Study Design / Methods

Although some understanding of the race-specific and vitamin D-driven biochemical mechanisms and pathways affecting prostate cancer (37) have been demonstrated, the main objective of this proposal is to fill existing gaps in knowledge by identifying those mechanisms and pathways that are especially relevant to explain vitamin D effects on prostatic cells and tissues, as well as on prostate cancer disparities between African American and Caucasian men. The proposed studies will employ advanced technologies to analyze transcriptional profiles and biological pathways in prostate tissue specimens from male subjects undergoing prostate biopsy, and will involve studies of gene expression profiles, derived from RNA-seq data. Comparison of these transcriptional and biological profiles between African American and Caucasian subjects will allow us to identify the critical transcription profiles in the prostate affected by race. Additionally the potential variations related to vitamin D levels (before and after supplementation) as well as serum ancestry markers will be explored.

Objective 1. To utilize RNA-seq analyses to further demonstrate and identify a specific stress pattern signal that exists between black and white men who are undergoing prostate biopsy. We have demonstrated that transcriptional profiles and biological pathways in the prostate are significantly different between African American and Caucasian subjects. The results of these studies will allow us to further elucidate the molecular underpinnings of health disparities in prostate cancer, including identification of specific stress patterns. These studies will involve purification of ribonucleic acid (RNA) from prostate tissue specimens obtained at prostate biopsy, RNA sequencing (RNA-seq), analyses of transcription profiles, and comparison of these profiles across race by advanced bioinformatics tools.

Patient Cohort: As discussed in the Background section, a substantial amount of information has already been collected through the pilot prostatectomy study as well as the initial aspects of this study. We have invested considerable resources to procure and analyze clinical samples obtained through our ongoing as well as previous research. This proposed study will leverage these investments and continue procuring and analyzing new samples that are annotated and linked with social determinants and allostatic load variables.

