Data Analytic Approaches: Fold-change (FC) estimation and hypothesis testing for differential expression will be performed using the DESeq2 Bioconductor library (43, 44, 39). DESeq2 models read counts as arising from a negative binomial distribution using a generalized linear model (GLM) approach that facilitates effect estimation of experimental design factors. DESeq2 conducts gene-specific comparisons between groups based on model-based linear contrasts, with inference based on associated two-sided Wald tests. For each gene, DESeq2 reports estimated FC, a p-value, and a q-value (45-47) equivalent to the smallest false discovery rate (FDR) incurred when declaring that test significant. We will control the FDR at 10%, but will consider less conservative FDR thresholds (e.g. 15% or 20%) if the number of significant genes is too small (e.g. <20). We will construct volcano plots – scatterplots of $-\log_{10}(p\text{-value})$ versus $\log_2(\text{FC})$ – to identify genes strongly associated with race identification or circulating levels of Vitamin D with high statistical significance. Additionally, we will analyze read counts using edgeR (41) to confirm DESeq2 results. Finally, we will utilize Cufflinks to assemble the alignments into a parsimonious set of transcripts (42). This analysis will complement the approach described above and provide further validation of differentially expressed mRNAs.

Analysis of Cumulative Molecular Data: The cumulative data will be analyzed to identify race-associated differences between tissue samples from African American and Caucasian subjects. Using the list of differentially expressed genes from Objective 1, regression coefficients, t-statistics and statistical significance (*p*-values) will be saved and volcano plots will

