- After analysis, the VA Laboratory will not store any remaining blood samples.
- Results will be entered into the research study data base with the assigned code by a Research Coordinator.
- Shared results will be with the assigned codes.

3) Allostatic load measurements: SBP/DBP (systolic and diastolic blood pressure), heart rate and waist/hip ratio are non-invasive measurements

- SBP/DBP and heart rate will be measured in the Urology Clinic prior to the prostate biopsy by either the Research Coordinator or Urology Clinic staff, and recorded in the VA CPRS electronic record as per Urology Clinic protocol prior to this Standard of Care procedure.
- The waist/hip ratio will be obtained using a designated tape measure by the Research Coordinator and recorded.
- These data will be entered in the study spreadsheet with the assigned codes.

4) A survey (Social Determinants) will be given to each subject with an instruction sheet and stamped, addressed return envelope to be completed at home after their prostate biopsy.

- The survey will be completed by subjects at home after their biopsy.
- The survey will be identified by each subject's assigned code.
- The survey will be mailed back to [name], VA HEROIC Investigator, for analysis and storage.
- Within 21 days if the survey has not been returned to the designated research staff, a research assistant will contact the subject to assess if they have completed the survey, or need additional assistance.
- Subjects will also be given the option to have the survey administered by telephone by a trained research assistant if they are having issues with self-administering the survey.
- Contact information for mailing the compensation gift card or verifying that the compensation has been received, will be destroyed once receipt of the gift card is documented.
- At the end of the study, these surveys will be boxed, labelled and sent to storage per VA Office of Research and Development's (ORD) Records Control Schedule.

5) Subjects will begin vitamin D₃ supplementation of 4000 IU daily.

- Previous studies have demonstrated no safety concern with this dose of vitamin D₃ supplementation.
- According to the Endocrine Society and Institute of Medicine standards, a vitamin D blood level between 30-50 ng/mL is sufficient. Taking 4,000 IU of vitamin D₃ daily will not exceed that level in the blood. Therefore, this research study amount of 4,000 IU daily should not produce any risk.

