12.0 Data Management

The study database spreadsheets

- The databases will be maintained in the VAMC Charleston secure (V:) drive and accessed only by the Research Coordinator(s) and the PI.
- All data entered will be with the assigned codes.
- All shared data will be with the assigned codes.

Sample Size Estimation: The sample size of this study is 250 (Part 1) and 60 (Part 2) based on practical considerations and reasonable statistical power. Our inferences will be based on the determination of threshold on *p*-values to achieve a false discovery rate (FDR) of 10%. We anticipate that the large majority of genes will not be significant, but do not know the *p*-value threshold; we expect it to be between 0.001 and 0.01. This sample size estimation is consistent with the data analytic approaches discussed under Study Design.

The primary endpoint is to estimate PSA reduction between pre and post treatment. We expect 20% PSA reduction posttreatment with the standard deviation of 40%. With 60 patients, the 95% confidence interval for the estimated PSA reduction is 10% to 30%.

Statistical Analysis

All statistical analyses will be performed using SAS v. 9.4 or R statistical analysis packages. The overall PSA reduction rate and the corresponding 95% confidence interval and percentage of each core from 12 cores will be estimated. Basic descriptive statistics will be estimated for demographic at pretreatment and clinical variables (blood pressure, weight, hips and waist circumference, vitamin D level, blood sugar, cholesterol, kidney function and stress hormones) at pre and post treatment.

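### Objective 1 looks for a stress signal, but no planned expression model contains race and a stress measure together, so a race difference alone cannot carry that label

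*Combined protocol and SAP*

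**What the plan says.** Objective 1 in section 1.0 is to "identify a specific stress pattern signal that exists between African American and Caucasian men who are undergoing prostate biopsy". The method given for it in section 10.0 is "comparison of these profiles across race by advanced bioinformatics tools".

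The gene-level analysis (section 10.0, Data Analytic Approaches) is meant "to identify genes strongly associated with race identification or circulating levels of Vitamin D with high statistical significance". Under Analysis of Cumulative Molecular Data, clustering is by race and treatment, and the random forests look for patterns by race.

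Stress is measured in two ways:

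- **Allostatic load.** Section 2.0 presents it as the gauge of each subject's stress and gives emphasis to HPA-related expression, "measurements of allostatic load and comparison of these profiles by race". Section 10.0, Allostatic Load Studies (under Objective 2), plans to correlate the health parameters of African American subjects with their molecular profiles. It also expects race differences in load to go with race differences in expression. The parameters are measured in Part 2 only.
- **Social Determinants survey.** Section 11.0, Part 2, item 4 states: "A survey (Social Determinants) will be given to each subject with an instruction sheet". It is completed at home after the biopsy.

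The Patient Cohort paragraph under Objective 1 speaks of "analyzing new samples that are annotated and linked with social determinants and allostatic load variables", without saying how the linked variables are analysed. The Statistical Analysis text in section 12.0 offers only this for such data: "Basic descriptive statistics will be estimated for demographic at pretreatment and clinical variables". The list that follows does not name the survey.

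**The concern.** The objective is worded as a finding about stress, while the specified contrast is between races. A gene can differ by race for many reasons, including ancestry, vitamin D status, tumour biology or tissue composition, and the contrast cannot separate these from stress.

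The pilot described in section 2.0 already reported 3107 genes differing by race at FDR<0.1. From two up-regulated genes, which an outside report had identified "as indicators of stress, because of a non-supportive family environment", it went on to suggest that the prostate is a sentinel organ for chronic stress. If the new trial repeats the race contrast without a stress term, the same inference can be drawn again without having been tested. The trial already collects what is needed to test it.

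**Working it through.** **1. Which variables enter each expression analysis**

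| Place in section 10.0 | Comparison factor | Stress term? |
|---|---|---|
| Objective 1, method | race | no |
| Data Analytic Approaches | race or vitamin D level | no |
| Cumulative data, clustering | race and treatment | no |
| Cumulative data, random forests | race | no |
| Allostatic Load Studies, correlation (Objective 2) | allostatic load parameters, African American men | yes, race held fixed; no model or error control of its own |
| Allostatic Load Studies, expectation (Objective 2) | race difference in load against race difference in expression | yes, but race not adjusted for |

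No row has race and a stress measure in one model.

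**2. What the planned within-group correlation can detect**

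The documents give no power figure for this question, so there is none to reproduce. Inputs from section 10.0: about 20 African American men (the stated 40% clinic share of 60 would be 24), and an expected p-value cut-off between 0.001 and 0.01.

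Detectable |r| at 80% power (Fisher z) = tanh[(z for the two-sided cut-off + 0.842)/√(n−3)].

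- n=20, p<0.01: tanh[(2.576+0.842)/√17] = tanh(0.829) = 0.68
- n=20, p<0.001: tanh[(3.291+0.842)/√17] = tanh(1.002) = 0.76
- n=24: 0.63 and 0.72

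**3. The same test with race in the model, all 60 Part 2 men**

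One covariate changes the divisor to √(n−4) = √56 = 7.48.

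- p<0.01: tanh(3.417/7.48) = tanh(0.457) = 0.43
- p<0.001: tanh(4.132/7.48) = tanh(0.552) = 0.50

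Power at a race-adjusted correlation of 0.40 (assumed; atanh = 0.424) is Φ(0.424×7.48 − z) = Φ(3.17 − z): 72% at p<0.01 and 45% at p<0.001. At 0.35 it is 56% and 29%. If only 42 men had the stress measure (an assumed 70% survey return), power at 0.40 falls to 51% and 25%.

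**4. Why the cross-race expectation does not separate stress from race**

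Assume 20 and 40 men, and a gene and a stress score that are unrelated within each race but differ between races by d₁ and d₂ SD. With pq = (1/3)(2/3) = 0.222, the pooled correlation is pq·d₁d₂/√[(1+pq·d₁²)(1+pq·d₂²)].

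- d₁=1, d₂=0.8: 0.178/√(1.222×1.142) = 0.15. A pooled test at 5% with n=60 has mean atanh(0.15)×√57 = 1.14, and flags the gene about 21% of the time.
- d₁=d₂=0.5: correlation 0.05, flagged about 7%.
- d₁=d₂=1: correlation 0.18, flagged about 28%.

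Simulation of the three cases agreed: about 22%, 7% and 29% without race in the model, and about 5% in each case with it.

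**The case against.** The strongest reply is that the protocol does have a stress measure and does plan to relate it to expression. Allostatic load is named as the gauge of stress, and a correlation within African American men holds reported race fixed. The heading it sits under matters less than the fact that it is planned, and the Patient Cohort paragraph ties samples to load within Objective 1. This stands. A reader might infer that the trial as a whole cannot tell stress from race; the documents do not support that, because the within-group correlation would give some evidence.

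A reader might also infer that every gene differing by race will be counted as stress. No passage says so. Section 2.0 gives emphasis to HPA-related profiles, and section 10.0 adds pathway enrichment, so Objective 1 can be read as a search for stress-related transcription that differs by race. Even then, pathway membership is not evidence that the men's stress drives the difference.

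Nor do the documents support treating the survey as the missing stress measure. They do not describe its content or say that it yields a stress score, and it is completed after the biopsy by men who have reached Part 2. Its absence from the Appendix 1 schedule looks clerical, since section 11.0 describes the procedure and section 13.0 lists it.

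Finally, high power of the race contrast for a gene that truly differs by race is not an error rate, and is not used here as a measure of the flaw.

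**Conclusion.** The point holds in a limited form. Objective 1's specified tests use race, with vitamin D level and treatment the only other named factors. The link from stress to expression is an unspecified correlation in about 20 men plus a cross-race expectation that race alone could satisfy. A race difference found under Objective 1 therefore cannot by itself be called a stress signal.

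In size, the planned correlation has 80% power only for |r| of about 0.68 to 0.76, against about 0.43 to 0.50 for a race-adjusted test in 60 men. These figures assume about 20 African American men, complete load data, the plan's expected cut-offs and approximate normality. The 7% to 28% range in step 4 depends on assumed race differences of 0.5 to 1 SD.

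The race-adjusted test is an improvement but not a powerful one: at r=0.40 it reaches 72% to 45%. The primary PSA endpoint is not affected. The change should be made because this is the first listed objective and the data are already to be collected.

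**What to change.** In section 10.0, Data Analytic Approaches, add for Objective 1:

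- Fix a stress/HPA gene list before sequencing.
- In all Part 2 men, fit baseline expression on race plus the baseline allostatic load score, with the false discovery rate controlled over that list.
- Add the Social Determinants survey score, defined in advance, as a secondary and supporting stress variable, not as the sole criterion.
- Describe a gene as stress-associated only if it is related to a stress measure with race in the model. Report genes that differ only by race as race-associated.

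Two clarifications go with this. Add the survey to the Appendix 1 schedule. Also state when baseline load is measured relative to the biopsy that yields the baseline core: section 10.0 and Appendix 1 place it at entry to Part 2, after that biopsy, whereas section 11.0 says before the biopsy, without saying which one. These passages must be reconciled.

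The cost is plan wording and one further model on data already to be collected. The list labelled stress will be shorter, the model covers Part 2 men only, men without a returned survey drop out of the secondary analysis, and adjustment for race may miss stress effects that vary mainly between races.
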